8.5.2. Self-Controlled Risk Interval design

[Table 3](#) shows the statistical power that can be obtained for a range of relative risks and a range of sample sizes. For example, a sample size of 100 cases either in the risk or control window will allow the detection of a relative risk equal to or greater than 2 with 93% statistical power.

Table 3: Detectable Relative Risk and Statistical Power for SCRI Design

Relative Risk	Sample Size*	Power
1.5	20	14.2%
2	20	32.0%
2.5	20	49.5%
3	20	63.8%
1.5	50	29.2%
2	50	66.7%

Table 3: Detectable Relative Risk and Statistical Power for SCRI Design

Relative Risk	Sample Size*	Power
2.5	50	88.1%
3	50	96.3%
1.5	100	51.9%
2	100	92.6%
2.5	100	99.4%
3	100	100.0%
1.5	150	69.2%
2	150	98.7%
2.5	150	100.0%
3	150	100.0%
1.5	200	81.2%
2	200	99.8%
2.5	200	100.0%
3	200	100.0%

*Sample size = number of events in risk and control window.

Table 4 shows the number of vaccinated individuals assuming the same time in the control and risk window to obtain an 80% statistical power for a range of relative risks. For example, a sample size of 69 vaccinated individuals with an AE of interest will allow the detection of a relative risk equal to or greater than 2 with 80% statistical power.

Table 4: Detectable Relative Risk and Sample Size for 80% Statistical Power for SCRI Design

Relative Risk	Individuals with AE of Interest	Power
1.5	195	80.0%
2	69	80.5%
2.5	41	80.9%
3	29	80.4%

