8.2. Setting and Study Population

8.2.1. Study Setting

For the implementation of the feasibility assessment, electronic health care databases in Southern and Western Europe that have shown interest and are members of the Vaccine Monitoring Collaboration for Europe (VAC4EU) will be used. The selected data sources and two-letter country codes are as follows:

- SIDIAP (Sistema d'Informació per el Desenvolupament de la Investigació en Atenció Primària) [Information System for Research in Primary Care] (ES)
- VID (La Fundació para el Fomento de la Investigación Sanitaria y Biomédica de la Comunitat Valenciana) [The Foundation for the Promotion of Health and Biomedical Research of Valencia Region] (ES).
- PHARMO DATABASE NETWORK (PHARMO Institute for Drug Outcomes Research) (NL)
- ARS Toscana (Agenzia Regionale di Sanità della Toscana) [a research institute of the Tuscany region of Italy] (IT)]. Since the approval of protocol version 2 by the EMA PRAC, a revision of the procedure for data access in the Tuscany Region has started. Hence, the study team at ARS Toscana has suspended its activities concerning the re-use of data until the revision of the procedures is complete. Until then ARS Toscana cannot contribute data to the study.

Further information on the data sources used in this study can be found in Section 8.4. When needed (based on specific safety concerns occurring in specific countries, or because of size) additional data sources may be added for dedicated evaluation studies, if they have adequate data on exposure, outcomes and covariates.

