8.4. Data Sources

The study will use data from secondary electronic health record databases that are population-based. All data sources will have the ability to provide data on COVID-19 vaccines, outcomes (diagnoses, procedures, laboratory results, and treatments), and important covariates. It is not currently known the extent to which COVID-19 vaccines, product types, and batch numbers will be captured in data sources. To be included in the study, data sources should preferably be updated at a minimum once every 3 months. At the proposal stage, members of VAC4EU (<https://vac4eu.org/>) were offered the option to participate in the study. Four data sources from 3 countries (Italy, Spain, and The Netherlands) countries will be included in the study. A more detailed description will be included in the [VAC4EU FAIR Catalogue that Molgenis](https://www.molgenis.org/) based (<https://www.molgenis.org/>).

When establishing the agreements with the data sources to conduct the study, it will be emphasized that the current list of AESIs may be expanded during the course of the study to accommodate newly identified AESIs.

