8.4.1. SIDIAP (ES) (7 million Active Individuals)

The Information System for Research in Primary Care (Sistema d'Informació per al Desenvolupament de la Investigació en Atenció Primària' [SIDIAP]; www.sidiap.org) was created in 2010 by the Catalan Health Institute and the IDIAP JGol Institute. It includes information collected since 01 January 2006 during routine visits at 278 primary care centres pertaining to the Catalan Health Institute in Catalonia (North-East Spain) with 3,414 participating GPs. SIDIAP has pseudo-anonymised records for 7 million people (80% of the Catalan population) and is highly representative of the Catalan population. The SIDIAP data comprise the clinical and referral events registered by primary care health professionals (e.g., GPs, paediatricians, and nurses) and administrative staff in electronic medical records, comprehensive demographic information, community pharmacy invoicing data, specialist referrals, and primary care laboratory test results. The SIDIAP data can also be linked to other data sources, such as the hospital discharge database, on a project-by-project basis. Health professionals gather this information using ICD-10-CM codes, ATC codes, and structured forms designed for the collection of variables relevant to primary care clinical management, such as country of origin, sex, age, height, weight, body mass index, tobacco and alcohol use, blood pressure measurements, and blood and urine test results. Regarding vaccinations, SIDIAP includes all routine childhood and adult immunisations, including the antigen and the number of administered doses. Encoding personal and clinic identifiers ensures the confidentiality of the information in the SIDIAP database. Currently, with the COVID-19 pandemic, there is the possibility to have shorter-term updates in order to monitor the evolution of the pandemic. Recent reports have shown the SIDIAP data to be useful for epidemiological research. SIDIAP is listed under the ENCePP resources database.

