8.7.1. Main Summary Measures

For the feasibility analysis the utilisation patterns of Ad26.COV2.S and other COVID-19 vaccines will be characterised and monitored over time. Description of demographics and clinical characteristics will be reported overall and for different groups of vaccine recipients.

The primary analysis will focus on calculating and comparing the incidence rates of each non-acute AESI between individuals exposed to Ad26.COV2.S and (1) unexposed individuals; (2) individuals exposed to another viral vector COVID-19 vaccine (i.e., Vaxzevria® [AZD1222] by Oxford/AstraZeneca); and 3) individuals exposed receiving a mRNA COVID-19 vaccine (cohort).

For acute events, the relative risk between risk window and control window will be estimated (using an SCRI design) among individuals exposed to Ad26.COV2.S. All analyses will be conducted within each data source and pooled across data sources using a random-effects model.

For the COVID-19 vaccines with a 2-dose schedule, AESI-specific risk windows after each dose of the comparator will be considered for the analyses. Further details on how to deal with different doses will be included in the SAP.

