8.7.1.3. Self-controlled Risk Interval Design**Descriptive Statistics**

The number of cases of each AESI will be reported in the control and risk windows, overall and by important covariates.

Measures of Association

Conditional Poisson regression will be used to estimate incidence rate ratios and 95% confidence intervals (CIs). The SCRI inherently adjusts for both measured and unmeasured time-constant factors such as sex and chronic health conditions with onset before the start of follow-up. Time-varying confounders (e.g., medications and other vaccinations) may be included as covariates in regression models. Subgroup analyses will be conducted by groups defined by demographic and clinical characteristics and other covariates of interest.

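### Tables 3 and 4 give SCRI power for one merged sample, but the plan pools source-specific estimates by random effects over about three sources, so the stated power is not that of the planned pooled analysis

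*Protocol*

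**What the plan says.** Section 8.5.2 gives SCRI power for a single count of cases. The footnote to Table 3 reads "Sample size = number of events in risk and control window", and Table 4 is introduced as "assuming the same time in the control and risk window to obtain an 80% statistical power for a range of relative risks". There are two worked examples. One is 100 cases for a relative risk of 2 with 93% power (92.6% in the table). The other is that "69 vaccinated individuals with an AE of interest will allow the detection of a relative risk equal to or greater than 2 with 80" per cent power (80.5% in the table). Neither the tables nor the text of 8.5.2 mentions data sources or variation between them.

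Section 8.7.1, directly after describing the SCRI comparison, says: "All analyses will be conducted within each data source and pooled across data sources using a random-effects model". The abstract repeats this. Section 8.4 lists four data sources, but 8.2.1 explains that data access in Tuscany is suspended and adds: "Until then ARS Toscana cannot contribute data to the study". That leaves SIDIAP, VID and PHARMO.

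**The concern.** A power table should describe the analysis that will be reported. Merging all cases into one sample and pooling three separate estimates by random effects are different analyses with different precision. With only three sources, the between-source variance is often estimated above zero by chance, which widens the pooled interval even when the true effect is the same everywhere. Any real heterogeneity widens it further.

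This is a safety study, so the stated power shapes what a reader expects a given number of cases to show. If 69 cases are taken as adequate to detect a doubling of risk when the pooled analysis would miss it about a third of the time, a null pooled result on an acute AESI looks more informative than it is.

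**Working it through.** **Inputs.** From the protocol: relative risks, case counts and stated power (Tables 3 and 4); equal risk and control windows (8.5.2); source sizes of 7, 5 and 2.5 million for the three contributing sources (8.4.1 to 8.4.3); random-effects pooling (8.7.1). Assumed, because the protocol does not give them: two-sided 5% level, inferred from the 95% intervals in 8.7.1.3; events divided in proportion to source size; DerSimonian-Laird with a normal interval; between-source SD of the log relative risk, tau, of 0 and 0.3.

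**Step 1: reproduce the printed figures.** For one sample with equal windows, a case falls in the risk window with probability p = RR/(1+RR). The signed-root likelihood-ratio formula is

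- A = 2[p ln RR − ln((RR+1)/2)]
- B = (ln RR)² p(1−p)/A
- power = Φ[(√(nA) − 1.96)/√B]

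For RR 2 and n = 69: p = 0.6667, A = 2(0.4621 − 0.4055) = 0.1133, √(69 × 0.1133) = 2.796, B = 0.4805 × 0.2222/0.1133 = 0.943 and √B = 0.971. Power = Φ[(2.796 − 1.960)/0.971] = Φ(0.861) = 80.5%, as printed. All four Table 4 rows, and every Table 3 row not rounded to 100.0%, reproduce to within 0.3 points. The tables are right for one merged sample.

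**Step 2: the pooled analysis.** In each of 40,000 simulated studies, cases were split multinomially 7:5:2.5. Risk-window cases in source i were binomial with p from that source's RR. The estimate was y = ln(a/b) with variance v = 1/a + 1/b, where a and b are the risk- and control-window counts and 0.5 was added to both if either was zero. With w = 1/v and k sources,

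- tau² estimate = max{0, [Q − (k−1)]/[Σw − Σw²/Σw]}
- w* = 1/(v + tau² estimate)
- detection if Σw*y/√Σw* exceeds 1.96

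| RR, cases | Stated | Fixed-effect pooling, tau 0 | DerSimonian-Laird, tau 0 | DerSimonian-Laird, tau 0.3 |
|---|---|---|---|---|
| 1.5, 195 | 80.0% | 78% | 68% | 47% |
| 2, 69 | 80.5% | 77% | 67% | 56% |
| 2.5, 41 | 80.9% | 72% | 63% | 57% |
| 3, 29 | 80.4% | 67% | 61% | 56% |
| 2, 100 | 92.6% | 91% | 83% | 67% |

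Figures are good to about a point. In the Table 4 rows the between-source variance came out above zero in 28–36% of runs although its true value was zero.

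**Step 3: a check by hand.** Fixed-effect power for RR 2 and 69 cases is close to Φ[ln 2 × √(69 × 2/9) − 1.96] = Φ(2.714 − 1.960) = 77.5%, which agrees with the simulated 77%.

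**Step 4: where the loss arises.** At 195 cases, about 2 of the 12 points lost come from inverse-variance pooling (80 to 78) and about 10 from the random-effects step (78 to 68). At 29 cases it is the other way round: about 13 of the 19 points are lost before any between-source variance enters (80 to 67) and about 6 after (67 to 61).

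**Step 5: sensitivity to what is not stated.** For RR 2 and 69 cases, four sources instead of three give 66% at tau 0 and 57% at tau 0.3. Knapp-Hartung with three sources gives about 30–34% in the Table 4 rows at tau 0. A one-stage random-effects binomial model with a Wald test gives about 75–79% in the 195-, 69- and 41-case rows, but a likelihood-ratio test of that model gives only about 60%. For 80% power at RR 2, DerSimonian-Laird needs about 95 cases at tau 0, 120 at tau 0.2 and 180 at tau 0.3, against the stated 69.

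**The case against.** The strongest reply is that nothing in Tables 3 and 4 is miscalculated and that no single pooled power figure follows from the protocol. Section 8.7 leaves details of data pooling to the SAP, so the missing estimator is not a defect. Section 9.1 makes sharing only coefficients conditional on privacy concerns, so a one-stage random-effects fit is not excluded, and its loss may be small. All of this stands. A reader might infer from the table above that the protocol's 80% is really some fixed lower figure, or that the authors made an arithmetic error. The documents support neither.

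It also stands that the SCRI tables are conditional grids (if so many cases, then this power). The study uses whatever cases the databases hold, so restated tables would change no recruitment number or stopping rule. Nor is power the only guide to a null result, because 8.7.1.3 reports incidence rate ratios with 95% intervals.

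What does not stand is reading the tables as power within one source. Section 8.5 sizes the study on about 18.1 million people, which is the sum of all four sources (7 + 5 + 2.5 + 3.6), and 8.5.2 gives no per-source split. Even on that reading, the pooled analysis would have no stated power.

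**Conclusion.** The point holds as a mismatch between the power basis and the planned analysis. Tables 3 and 4 and both worked examples describe one homogeneous merged sample; 8.7.1 commits the study to random-effects pooling of source-specific estimates, currently from three sources.

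The size of the gap is conditional. Under two-stage DerSimonian-Laird with a normal interval, a 7:5:2.5 split and no true heterogeneity, the chance of missing a doubling of risk with 69 cases rises from about 20% to about 33%. Real heterogeneity or a Knapp-Hartung interval makes it worse, and a one-stage random-effects fit with a Wald test makes it milder. It would be wrong to attribute the whole loss to the between-source variance: in the 41- and 29-case rows half or more comes from inverse-variance pooling of small counts. The point merits correction but does not threaten the validity of the estimates.

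**What to change.** Do one of two things in 8.5.2:

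- Restate Tables 3 and 4 and both worked examples for the random-effects analysis actually planned, naming the estimator, the interval method, the number of sources and the assumed between-source SD. Under DerSimonian-Laird at tau 0, for example, the RR 2 row would read about 95 cases rather than 69.
- Keep the tables, label them as power for a single merged sample, and add the pooled-analysis figures beside them under the same stated assumptions, preferably for more than one value of tau.

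The cost is a short simulation and revised text; no data collection changes. A one-stage conditional Poisson estimate over all cases could be added as a supportive analysis. Each case is its own control, so differences in baseline rates between sources cancel, and the unadjusted fit needs only window counts per source. Making it primary is optional and is a trade-off: it would match the printed tables but give up the allowance for heterogeneity between databases that 8.9 itself describes as heterogeneous.

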8.6. Data Management

This study is conducted in a distributed manner using a common protocol, common data model (CDM), and common analytics programs (Figure 3) The data pipeline has been developing from the EU-ADR project and was further improved in the IMI-ConcePTION project (<https://www.imi-conception.eu/>) and used to generate background rates in the ACCESS project. This process maximises the involvement of the data providers in the study by utilising their knowledge of the characteristics and the process underlying the data collection which makes analysis more efficient.

8.6.1. Data Extraction

Each database access provider (DAP) creates extraction, transform, and load (ETL) specifications using the standard ConcePTION ETL design template (accessible via this link: <https://docs.google.com/document/d/1SWi31tnNJL7u5jJLbBHmoZa7AvfcVaqX7jiXgL9uAWg/edit>) and upload it to the VAC4EU FAIR Catalogue.

The most recent version of the ConcePTION CDM (2.2) will be used for this analysis.

Following completion of this template and review with study statisticians and principal investigators, each DAP extracts the relevant study data locally using their software (e.g., Stata, Statistical Analysis Software [SAS], R, Oracle). These data are loaded into the CDM structure in CSV format. These data remain local (Figure 3).

8.6.2. Description of Data Transformation and Analysis Pipeline

This study uses data that is already collected for analysis and available in electronic health care data sources in 4 EU countries and follows the following principles.

First, to harmonise the structure of the data sets held by each partner, a shared syntactic foundation is utilised, the CDM will be used that was developed in the IMI-ConcePTION project. In this CDM, data are represented in a common structure, but the content of the data remains in their original format. The ETL design is made available on paper and later on in the VAC4EU FAIR Catalogue. The validity of the ETL will be assessed using Level 1 (completeness) and Level 2 (logical consistency) R-scripts that have been developed as part of the IMI-ConcePTION project.

Second, to reconcile differences across terminologies a shared semantic foundation is built for the definition of events under study by collecting relevant concepts in a structured fashion using a standardised event definition template. The Codemapper tool (<https://vac4eu.org/codemapper/>) was used to create diagnosis code lists based upon completed event definition templates for each event and comorbid risk condition in the ACCESS-BGR protocol (Zenodo.org).

Based on the relevant diagnostic medical codes, as well as other relevant concepts (e.g., medications), algorithms were constructed to operationalise the identification and measurement of each event. These algorithms may differ per data source, as the components that go into the study variable may differ. Wherever possible the event definition sheet specifies prior validation of algorithms and codes for benchmarking. Scripts for semantic harmonisation are created centrally and provided in R and distributed to data access providers for local deployment. This will result in a set of study variables which are both semantically and syntactically harmonised. The quality of the semantic harmonisation will be assessed using Level 3 checks and compared against published rates and between databases (benchmarking). Limited to outcomes, components will be analysed in each data source, to assess the unique contribution of each data bank, therefore providing evidence on the sensitivity and accuracy of the algorithms. Results from validation activities will be used to inform the calculation of the validity of the composite algorithms.

Third, following conversion to harmonised study variable sets, additional R- or SAS-scripts for the calculation of analytical datasets are distributed to data access providers for local deployment. The output datasets produced by these scripts are then uploaded to the Digital Research Environment (DRE) for pooled analysis of incidence and visualisation (Figure 3). The DRE is made available through UMCU/VAC4EU (<https://www.andrea-consortium.org/>). The DRE is a cloud-based, globally available research environment where data are stored and organised securely and where researchers can collaborate (<https://www.andrea-consortium.org/azure-dre/>).

[figure not shown]
All final statistical computations are performed on the DRE using R and SAS. Data access providers have access to the project workspace for verification of the results.

8.6.3. Data Access

Within the DRE, each project-specific area consists of a separate secure folder called a “workspace.” Each workspace is completely secure, and researchers are in full control of their data. Each workspace has its own list of users, which can be managed by its administrators. The DRE architecture allows researchers to use a solution within the boundaries of data management rules and regulations. Although General Data Protection Regulation and Good (Clinical) Research Practice still apply to researchers, the DRE offers tools to more easily control and monitor which activities take place within projects. All researchers who need access to the DRE are granted access to study-specific secure workspaces.

Access to this workspace is only possible with double authentication using an identification code and password together with the user’s mobile phone for authentication. Upload of files is possible for all researchers with access to the workspace within the DRE. Downloading files is only possible after requesting and receiving permission from a workspace member with an “owner” role.

Figure 3: Data Transformation and Flow

8.6.4. Data Processing

Due to the nature of the study, a repeated data processing procedure is envisioned, based on the pipeline described in the previous section. This allows for optimising the data processing timelines and archiving procedures (see Section 8.6.6).

In the study start, a baseline data extraction will be made by each of the DAPs. This creates a baseline instance of the data source. This is ETL’ed into the ConcePTION CDM and forms the baseline instance of the CDM. The data pipeline will be run for the first time on the baseline instance of the CDM of each DAP, and produce a baseline set of analytic datasets that will be centrally analysed for the baseline assessment.

Periodically (every 4 months), DAPs are requested to perform the extraction of the new data, which will be called the x^{th} supplementary instance of their data source. The supplementary instance of the data source will be ETL'ed to the ConcePTION CDM, to form a supplementary instance of the CDM, which will be analysed, this instance comprises all the prior data.

8.6.5. Case Report Forms/Data Collection Tools

This study will use secondary data collected in electronic health record databases. For the purpose of validating selected study endpoints, special forms may need to be developed and securely saved in environments assuring data protection and patient confidentiality according to the requirements of each country and DAP.

8.6.6. Record Retention

DAPs are responsible locally to archive each data source instance that is used for the study. The meta-data table in the CDM allows for storing details on the data source instance. The DAP has the obligation to archive the data source instances, the ETL scripts, the R-scripts that were used and the results that were uploaded to the DRE, locally.

Aggregated results from DAPs, ETL design documents, and a repository of study scripts will be stored in the DRE for inspection by the study sponsor for at least five years. The final study aggregated results sets and statistical programs to pool and visualise will be archived and stored on the DRE for five years.

Documents that individually and collectively permit evaluation of the conduct of a study and the quality of the data produced will be retained for a period of 5 years in accordance with Good Pharmacoepidemiology Practices (GPP) guidelines. Study records or documents may also include the analysis files, syntaxes (usually stored at the site of the database), ETL specifications, and output of data quality checks.

After 5 years all materials from the DRE will be retained for at least 15 years on a UMCU secure drive. The final study protocol and possible amendments, the final statistical report, statistical programs and output files will be archived on the UMCU secure drive according to Julius Clinical standard operating procedures.

